## **Background and Significance**

Occupational Therapy (OT) is one of the mental health services. The service phase includes acute/chronic hospitalization, daycare centers (adolescents, adults, and the elderly), community mental rehabilitation institutions, psychiatric nursing home, and outpatient assessment/treatments. OT provides holistic and continuous mental rehabilitation services at each stage of mental health care. During the acute hospitalization and based on the Model of Human Occupation (MOHO) model, the occupational therapist provides daily activities to assist acute patients with mental illness to develop occupation adaptation to enable and prepare for discharge.

However, the lack of a client-centered OT service model limits the interpretation of the treatment effect and the process of change. This will seriously affect the integrity and continuity of OT services and will limit the development of OT professions.

## **Specific Aims**

The purpose of the study is to develop and validate Client-centered Occupational Therapy Service at Taipei City Psychiatric Center (OT@tcpc) service model to assist clinicians to provide and integrate comprehensive OT services.

## **Research Design and Methods**

Participants who met the inclusion criteria and signed the informed consent were assessed twice, 2 weeks apart, by an occupational therapist in a quiet environment. After the assessment, participants were randomized into two groups in a blinded one-to-one fashion. This project consists of 2 stages. First, based on the MOHO model we use 6 courses with 2 weeks program to develop the OT@tcpc service model. Second, validate two indicate the occupation identity and competence to validate the OT@tcpc service model. We will recruit 70 inpatients with schizophrenia and divided into intervention group, based on MOHO theory, and control group. The Intervention group provided Occupational therapy based on the MOHO theory, while the control group adopted the original Occupational therapy model.

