### **Inclusion Criteria:**

[figure not shown]
1. Patients diagnosed with schizophrenia according to DSM-5 diagnostic criteria.
2. Aged 20 or older
3. Agree to participate in the study and provide a signed informed consent form

(ICF)

[figure not shown]
Exclusion Criteria:

1. Diagnosis of intellectual developmental disorders
2. History of severe brain injury
3. Cannot complete the study due to poor cognitive, vision or hand function

The first patient was included in the study June 2020 and the last patient exited the study in July 2020. The recruitment period was one week. The trial was conducted at Songde District of Taipei City Hospital in Taiwan. A total of 35 patients were screened (Fig 1). The planned study period was 1 month. The trial was designed according to Fig 2.

**Fig1. Patient flow.** The outline of the selection and randomization flow of patients in the study.

**Fig 2. Trial design.** Patients with chronic schizophrenia were randomized to the two treatment arms at the Baseline.

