#### Statistical methods:

Descriptive summary statistics or frequency counts of demographic and baseline data were presented by treatment arm and overall for the intent to treat (ITT) and per protocol (PP) populations. The PP population was defined as individuals who had completed all scheduled study visits, while the ITT referred to those with data from at least two study visits.

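### Does the order of sentences in Research Design and Methods mean that both assessments came before randomisation, leaving no post-treatment outcome?

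*Combined protocol and SAP*

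**What the plan says.** Research Design and Methods states that consented participants "were assessed twice, 2 weeks apart, by an occupational therapist in a quiet environment". The next sentence reads "After the assessment, participants were randomized into two groups in a blinded one-to-one fashion". The same section gives the programme length, in describing the first stage of the project: "we use 6 courses with 2 weeks program to develop the OT@tcpc service model". It names occupational identity and competence as the two validating indicators, but does not say at which assessment they serve as outcomes.

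The caption to Fig 2, at the end of the Inclusion Criteria section, says: "Patients with chronic schizophrenia were randomized to the two treatment arms at the Baseline". The text just above it refers the reader to Fig 2 for the trial design, reports a one-week recruitment period, and adds: "The planned study period was 1 month". First inclusion was in June 2020 and last exit in July 2020.

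The Statistical methods section defines the populations by visits. The per-protocol set is "individuals who had completed all scheduled study visits", while "the ITT referred to those with data from at least two study visits". It does not list the visits.

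**The concern.** A reader who takes the two sentences in Research Design and Methods in sequence finds two assessments, then randomisation. The caption to Fig 2 seems to say something else, because randomising at baseline would ordinarily leave the second assessment after allocation. Nothing in the readable text settles the matter by naming the outcome time point.

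Under the literal order, with only the two described assessments, every identity and competence score would predate treatment. The arms could then differ only by chance and by the balance of allocation, and no effect of the new service model could be estimated. The visit-based population rule adds to the unease, since two visits completed before allocation would satisfy the ITT definition with no post-treatment score.

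**Working it through.** The plan gives no figure to reproduce here. The check is to set the statements side by side and see which sequence they fit.

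**Inputs**
- Two assessments, 14 days apart (Research Design and Methods).
- Programme of 2 weeks, or 14 days (same section, given for stage 1). I assume that treatment in the trial lasts equally long.
- Recruitment of one week, or 7 days (Inclusion Criteria section).
- Planned period of 1 month, taken as 30 to 31 days (same section).

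**Sequence A:** assessment 1, randomisation, programme, assessment 2.
- Per patient: 14 days, because the programme fills the gap between assessments.
- From first recruitment to last exit: 7 + 14 = 21 days.
- Assessments before and after allocation: 1 and 1.

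**Sequence B:** assessment 1, assessment 2, randomisation, programme.
- Per patient: 14 + 14 = 28 days.
- From first recruitment to last exit: 7 + 28 = 35 days.
- Assessments before and after allocation: 2 and 0.

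**Against the planned month.** A fits with recruitment counted (21 < 30). B runs over by 35 − 31 = 4 to 35 − 30 = 5 days with recruitment counted, but fits if the month is per patient (28 < 30). The June-to-July 2020 calendar, at most 30 + 31 = 61 days, excludes neither. The timeline therefore leans towards A but does not decide it.

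**Against the wording**
- The randomisation sentence uses a singular noun after a sentence that summarises two assessments. If it means the first, it agrees with the Fig 2 caption.
- The caption does not strictly contradict B. Baseline is not defined, and allocation straight after a second pre-treatment assessment could also carry that name.
- The interval between assessments equals the programme length. A explains this directly; B would need a separate reason for a two-week run-in, and the document gives none.
- Statistical methods promises baseline data by arm. Table 1 gives one set of scores per arm, including occupational identity (24.9 ± 4.8 intervention, 25.7 ± 3.4 control) and competence (20.7 ± 2.6 and 22.1 ± 2.7), alongside the demographics. A single baseline set fits A. Table 1 does not name the assessment, so this supports A without proving it.

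**Against the population rule.** An ITT participant with no post-treatment score requires either B itself or a third visit added to B. No readable section describes a third visit. Under A, a participant with data from both visits has a post-allocation score. With two scheduled visits the ITT and per-protocol sets would coincide only if having data from a visit is the same as completing it, which the document does not say. That question would arise whatever the order of randomisation, so it does not bear on this point.

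**The case for a change.** The best case for asking for a correction is that the place of randomisation relative to outcome measurement is too basic to be left to a singular noun. The readable text never names the outcome time point. The interval of two weeks fixes the assessments relative to each other, but to neither allocation nor the end of the programme. Neither the visit-based definitions nor Table 1 fills the gap. The remedy would be cheap, and if the literal order was really followed, the consequence is as serious as it can be for a comparative trial.

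Part of this stands. The sentence order is ambiguous, the outcome assessment is not named in the text that can be read, and a clearer sentence would help any reader.

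It does not carry as far as a change to the plan. The trial's design is referred to Fig 2, which could not be seen, so the schedule cannot be called absent. The severe consequence arises only under the reading that the spacing, the timeline and Table 1 make the less likely one. On the likelier reading, rewording would leave every procedure, data point, analysis and conclusion as it is.

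**Conclusion.** This is loose drafting that an analyst would resolve sensibly, by treating the first assessment as baseline and the second, two weeks later, as the outcome. On that reading one assessment falls after allocation, the arms can be compared, and the trial takes 21 days including recruitment against a planned 30 to 31. The literal reading would leave no assessment after allocation and take 35 days.

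The conclusion rests on three assumptions: that the two-week programme described for stage 1 is also the treatment length in the trial, that the singular noun refers to the first assessment, and that Fig 2 shows nothing to the contrary. None is proved by the readable text, but nothing in it contradicts them. If it emerged that no assessment followed allocation, rewording could not repair that, and no treatment-effect claim would be tenable. As the document stands, no change to the plan is called for.

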### **Participants:**

Individuals with schizophrenia were recruited from the Songde District of Taipei City Hospital in Taiwan in June 2020.

### **Inclusion Criteria:**

[figure not shown]
1. Patients diagnosed with schizophrenia according to DSM-5 diagnostic criteria.
2. Aged 20 or older
3. Agree to participate in the study and provide a signed informed consent form

(ICF)

[figure not shown]
Exclusion Criteria:

1. Diagnosis of intellectual developmental disorders
2. History of severe brain injury
3. Cannot complete the study due to poor cognitive, vision or hand function

The first patient was included in the study June 2020 and the last patient exited the study in July 2020. The recruitment period was one week. The trial was conducted at Songde District of Taipei City Hospital in Taiwan. A total of 35 patients were screened (Fig 1). The planned study period was 1 month. The trial was designed according to Fig 2.

**Fig1. Patient flow.** The outline of the selection and randomization flow of patients in the study.

**Fig 2. Trial design.** Patients with chronic schizophrenia were randomized to the two treatment arms at the Baseline.

#### Statistical methods:

Descriptive summary statistics or frequency counts of demographic and baseline data were presented by treatment arm and overall for the intent to treat (ITT) and per protocol (PP) populations. The PP population was defined as individuals who had completed all scheduled study visits, while the ITT referred to those with data from at least two study visits.

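### The set called ITT is defined by having data from two or more visits, not by randomisation, so a randomised participant with data from fewer than two visits is left out

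*Combined protocol and SAP*

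**What the plan says.** Statistical methods defines two sets. For per protocol: "The PP population was defined as individuals who had completed all scheduled study visits". For intention to treat: "while the ITT referred to those with data from at least two study visits". Neither definition mentions randomisation or assigned arm, and no other section of the readable text defines a set of all randomised participants. The one use given for the sets is descriptive: "Descriptive summary statistics or frequency counts of demographic and baseline data were presented by treatment arm and overall".

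On timing, Research Design and Methods says that participants "were assessed twice, 2 weeks apart, by an occupational therapist in a quiet environment", and then: "After the assessment, participants were randomized into two groups in a blinded one-to-one fashion". The Fig 2 caption says: "Patients with chronic schizophrenia were randomized to the two treatment arms at the Baseline". The visit schedule may be in Fig 2 and the patient flow in Fig 1. Neither figure is available here, so nothing below treats the schedule or the flow as missing from the plan.

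The text reports 35 people screened, and 17 (intervention) and 16 (control) in the arms. Table 1 uses 17 and 16 without naming the analysis set.

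**The concern.** Readers take ITT to mean everyone randomised, analysed in the arm assigned. A set selected on data collected after randomisation is something else, because it can lose people for reasons related to treatment or outcome. If that set carried the between-arm comparison, such losses would be hidden behind a label that says there were none. With 16 or 17 people per arm, one person is about 6% of an arm.

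The second problem is redundancy. Two analysis sets are useful when they can differ. If only two visits were scheduled, the two definitions pick out essentially the same people, and showing both tells the reader nothing about sensitivity to dropout.

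**Working it through.** **1. Who is in each set.** Let k be the number of scheduled visits. The table shows the number of visits with data that qualifies a person for each set. It treats a visit with data as a completed visit, which is why the sets at k = 2 are called essentially, not exactly, the same.

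| k | ITT as defined | PP | In ITT but not PP |
|---|---|---|---|
| 2 | 2 | 2 | nobody |
| 3 | 2 or 3 | 3 | those with 2 |
| 4 | 2, 3 or 4 | 4 | those with 2 or 3 |

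For every k, a person with data from 0 or 1 visit is outside ITT, randomised or not.

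**2. Whether someone lost after baseline is excluded.** This depends on what counts as a visit.
- If the two assessments are the only visits and randomisation is at baseline (Fig 2 caption), a person who misses the second assessment has one visit and is excluded.
- If screening and baseline are separate visits with data (k = 3 with one follow-up), the same person has two visits and is included.
- If both assessments came before randomisation, as Research Design and Methods literally reads, every randomised person assessed as described already has two visits. That reading leaves no post-treatment measure and conflicts with the Fig 2 caption.

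**3. Counts.** 17 + 16 = 33, and 35 − 33 = 2. The number randomised is not stated in the readable text. If 0, 1 or 2 of these two people were randomised and then dropped by the rule, the loss is 0/33 = 0%, 1/34 = 2.9% or 2/35 = 5.7% of those randomised.

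**4. Illustrative bias if the 33 are the ITT set.** The plan gives no figure to reproduce. The assumptions, none of them from the documents, are an outcome gap g between people kept and people lost, and a normal-theory comparison of means. With m1 lost from intervention and m0 from control:

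bias = g1 × m1/(17 + m1) − g0 × m0/(16 + m0)

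SE = √(1/17 + 1/16) = 0.348 SD

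| Lost (intervention, control) | Gap | Size of bias | Bias/SE |
|---|---|---|---|
| 0, 0 | any | 0 | 0 |
| 1, 1 | 1 SD, same sign | 1/17 − 1/18 = 0.003 SD | 0.01 |
| 2, 0 | 1 SD | 2/19 = 0.105 SD | 0.30 |
| 0, 2 | 1 SD | 2/18 = 0.111 SD | 0.32 |
| 1, 1 | 1 SD, opposite signs | 1/18 + 1/17 = 0.114 SD | 0.33 |

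With b = bias/SE, the true level of a nominal two-sided 5% test is 1 − [Φ(1.96 − b) − Φ(−1.96 − b)]. At b = 0.319 it is 6.2%. Halving the gap to 0.5 SD for two lost from control gives 0.056 SD, b = 0.159 and 5.3%.

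To express this in scale points, the baseline SDs in Table 1 stand in for outcome SDs, which is a further assumption:
- Occupational Identity: √((16 × 4.8² + 15 × 3.4²)/31) = 4.18, and 0.111 × 4.18 = 0.46 points.
- Occupational Competence: √((16 × 2.6² + 15 × 2.7²)/31) = 2.65, and 0.111 × 2.65 = 0.29 points.

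**5. Illustrative bias if the 33 are everyone randomised.** The rule then removes people from within the 33; how many is unknown. At a 1 SD gap, per person:
- One of 17 (intervention): 1/17 = 0.059 SD; SE = √(1/16 + 1/16) = 0.354; b = 0.17; test level 5.3%.
- One of 16 (control): 1/16 = 0.063 SD; SE = √(1/17 + 1/15) = 0.354; b = 0.18; test level 5.4%.

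**The case against.** The strongest reply is that nothing has been shown to go wrong. Statistical methods ties the sets only to demographic and baseline summaries, and the readable text specifies no between-arm outcome comparison or its analysis set. A biased estimate would need three things that the documents do not show: this set used for an outcome test, a randomised person with fewer than two visits, and outcomes that differ between those lost and those kept. All of that stands, and it limits the point to a mislabelled definition with a conditional consequence.

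The illustration is also open to challenge. The gap is assumed. The only tests the document names are Wilcoxon and Fisher, for Table 1, so the normal-theory error rates indicate scale only. Same-sign gaps do not bound the bias, which is why the opposite-sign row is included.

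A reader might go further in two ways, and neither is supported. One is to infer that anyone with baseline data only is excluded. The documents do not equate assessments with study visits, so separate screening and baseline visits could keep such a person in. The other is to infer that the two people between 35 screened and 33 in the arms were randomised and then dropped. They may have failed screening, and the flow figure is not available to settle it.

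The literal order in Research Design and Methods does not rescue the rule. Even if nobody could then be excluded, membership would still not be defined by randomisation.

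**Conclusion.** Wrong as written, and minor. What is established from the text alone is that the set called ITT is selected on data availability, and that it leaves out any randomised participant with data from fewer than two visits. That it nearly coincides with the per-protocol set holds if the two described assessments are the only scheduled visits.

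No exclusion and no bias are demonstrated. If the two unaccounted-for people were never randomised, they contribute no bias. If both were randomised and lost, a 1 SD gap gives at most about 0.11 SD, under a third to a third of a standard error. Confidence is high about the wording of the rule. The size rests on the assumed gap, the comparison of means and the use of the set for outcomes.

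**What to change.** Under Statistical methods:

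1. Define ITT as all randomised participants, analysed in the arm assigned, whatever visits they attended, and use that set for the between-arm comparison.
2. Rename the present set for what it is: participants with data from two or more visits.
3. State on Table 1 which set its 17 and 16 represent.
4. Only if a randomised participant lacks the second assessment, add one sensitivity analysis that includes them, for example multiple imputation from baseline.

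The cost is a few lines of wording and one table label, with no new data. The downside is slight extra analysis work if step 4 applies, and participants with baseline data only add little information on the treatment effect.

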#### Statistical Analysis

A total of 35 patients were screened for participation in the study. One group of 16 people participated in the control group, and the other 17 people participated in the intervention group. In the sample for Intervention group, the mean age was 43.6 years (SD 9.0), and 64.7% of the participants were male. The average duration of illness was 23 years. In the sample for control group, 50% of the participants were also male, the mean age was 43.4 years (SD 9.4), and the average duration of illness was 24.4 years. These two groups were similar in terms of age, onset age, duration of illness, gender, education and marriage. Table 1 presents further details of the participants.

Measure	Intervention group (n=17)	Control group (n=16)	p value
	N (%), Mean $\pm$ SD		
Demographic characteristics			
Age (years)	43.6 $\pm$ 9.0	43.4 $\pm$ 9.4	0.93
Onset age (years)	20.1 $\pm$ 4.8	19.0 $\pm$ 3.8	0.47
Duration of illness (years)	23.0 $\pm$ 8.6	24.4 $\pm$ 8.6	0.65

Gender			0.49
Male	11 (64.7%)	8 (50.0%)	
Female	6 (35.3%)	8 (50.0%)	
Education			0.46
Junior high school	1 (5.9%)	3 (18.8%)	
Senior high school	7 (41.2%)	7 (43.8%)	
College and above	9 (52.9%)	6 (37.4%)	
Marriage			0.51
Single	15 (88.2%)	14 (87.5%)	
Married	2 (11.8%)	1 (6.3%)	
Divorced	0 (0.0%)	1 (6.3%)	
Medical characteristics			
MMSE	27.5 ± 2.5	27.8 ± 2.5	0.80
CGIS	3.6 ± 1.2	3.4 ± 1.6	0.58
LIADL	18.1 ± 4.8	17.8 ± 4.2	0.88
COTES	70.8 ± 7.9	74.9 ± 7.8	0.14
COPM-C	11.3 ± 5.4	9.9 ± 4.6	
COPM-C performance	5.7 ± 2.6	5.1 ± 2.3	
COPM-C satisfaction	5.6 ± 3.0	4.8 ± 2.5	
PSP	52.1 ± 15.9	51.9 ± 12.5	0.97
Socially useful activities	2.5 ± 1.5	2.3 ± 1.1	
Personal and social relationships	3.9 ± 1.3	4.3 ± 1.0	
Self-care	1.4 ± 0.7	1.4 ± 0.7	
Disturbing and aggressive behaviors	1.3 ± 0.5	1.4 ± 0.5	
OPHI-II	66.2 ± 8.0	69.4 ± 6.8	0.24
Occupational Identity	24.9 ± 4.8	25.7 ± 3.4	0.58
Occupational Competence	20.7 ± 2.6	22.1 ± 2.7	0.13
Occupational Behavior			
Settings	20.7 ± 2.7	21.6 ± 2.3	0.28

**Table 1. Demographic and medical characteristics for the two treatment groups.**

The sample statistics presented in this table were mean ± standard deviation (SD) for continuous variables and frequency (percentage, %) for categorical variables. The listed *p*-values of statistical tests were calculated using the Wilcoxon rank-sum test for continuous variables and the Fisher's exact test for categorical variables.

